10.2.13 Best Corrected Distance Visual Acuity: Effectiveness Assessment

Measure and record binocular ETDRS BCDVA at 4 m. This assessment must be performed by delegated trained masked assessor only.

10.2.15 Distance Corrected Intermediate Visual Acuity: Effectiveness Assessment

Measure and record binocular **ETDRS** DCIVA at 66 cm. This assessment must be performed by delegated trained masked assessor only.

10.2.17 Distance Corrected Near Visual Acuity: Effectiveness Assessment

Measure and record binocular **ETDRS** DCNVA at 40 cm. This assessment must be performed by delegated trained masked assessor only.

10.2.19 Contrast Sensitivity: Safety Assessment

Measure and record both binocular and first eye monocular contrast sensitivity under mesopic lighting conditions with and without glare. This assessment must be performed by delegated trained masked assessor only. Refer to MOP for details.

10.2.20 Adverse Event Collection: Safety Assessment

Assess and record any adverse events that are observed or reported since the time of consent.

AEs must be recorded for all enrolled subjects from the time of signature of informed consent, regardless of subject enrollment status (screen failure).

10.2.21 Device Deficiencies: Safety Assessment

Assess and record any device deficiencies that are reported or observed since the time of consent. Requirements for reporting device deficiencies in the study can be found in Section 11.

Device deficiencies must be recorded for all enrolled subjects from the time of signature of informed consent, regardless of subject enrollment status (screen failure).

10.3 Unscheduled Visits

If a subject visit occurs between any regularly scheduled visit and the visit is conducted by study personnel, this visit must be documented as an Unscheduled Visit. If the subject seeks medical attention outside the clinic (for example, at an emergency room) or at the clinic but is seen by non-study personnel, the investigator is to capture adverse event-related information on the adverse event form upon becoming aware.

During all unscheduled visits, the investigator must conduct the following procedures:

- Collect adverse event information
- Record changes in medical condition or concomitant medication

The investigator may perform additional procedures for proper diagnosis and treatment of the subject (e.g., subjective VA, slit lamp exam, tonometry, and dilated fundus exam). The investigator must document this information in the subject's case history source documents.

10.4 Discontinued Subjects

10.4.1 Screen Failures

Subjects who were excluded from the study after signing the informed consent, excluded based on inclusion/exclusion criteria at the Screening Visit, and prior to Visit 1 testing.

The investigator must document the reason for screen failure in the subject's case history source documents.

Subject numbers must not be reused.

10.4.2 Discontinuations

Discontinued subjects are individuals who voluntarily withdraw or are withdrawn from the study by the investigator after inclusion/exclusion criteria has been met at Screening Visit.

Subject numbers of discontinued subjects must not be reused (i.e., subject replacement is not allowed).

Subjects may discontinue from study or study treatment at any time for any reason. Subjects may also be discontinued from study treatment at any time if, in the opinion of the investigator, continued treatment poses a risk to their health.

The investigator must document the reason for study or treatment discontinuation in the subject's case history source documents.

To ensure the safety of all subjects who discontinue early, investigators must assess each subject and, if necessary, advise them of any therapies and/or medical procedures that may be needed to maintain their health.

10.4.3 Schedule of Procedures and Assessments for Subjects Discontinued from Investigational Product

Not applicable

10.5 Clinical Study Termination

The study sponsor reserves the right to suspend or close the investigational site or suspend or terminate the study in its entirety at any time.

If the clinical study is prematurely terminated or suspended by the study sponsor:

- The study sponsor must:
 - Immediately notify the investigator(s) and subsequently provide instructions for study termination.
 - Inform the investigator and the regulatory authorities of the termination/suspension and the reason(s) for the termination/suspension.
- The investigator must:
 - Promptly notify the IRB/IEC of the termination or suspension and of the reasons.
 - Provide subjects with recommendations for poststudy treatment options as needed.

The investigator may terminate the site's participation in the study for reasonable cause.

10.5.1 Follow-up of subjects after study participation has ended

Following this study, the subject will return to their eye care professional for their routine eye care.

11 ADVERSE EVENTS AND DEVICE DEFICIENCIES

11.1 General Information

An AE is any untoward medical occurrence, unintended disease or injury, or untoward clinical signs (including abnormal laboratory findings) in subjects, users, or other persons, whether or not related to the investigational medical device. Refer to the Glossary of Terms and figures below for categories of AEs and SAEs.

Specific Events Relevant to this Protocol

In addition to reporting all AEs (serious and nonserious) meeting the definitions, the investigator must report any occurrence of the following as an SAE:

- Cystoid macular edema
- Hypopyon
- Endophthalmitis
- Lens dislocation from posterior chamber
- Pupillary block
- Retinal detachment

Any other potentially sight-threatening event may also be considered serious based on the judgment of the investigator and should be reported appropriately as delineated in Section 11.3 (Procedures for Recording and Reporting).

Device Deficiencies

A device deficiency may or may not be associated with subject harm (i.e., ADE or SADE); however, not all ADEs or SADEs are due to a device deficiency. The investigator should determine the applicable category for the identified or suspect device deficiency and report any subject harm separately. Examples of device deficiencies include the following:

- Failure to meet product specifications (e.g., incorrect IOL power)
- IOL defect
- Scratched IOL
- Lack of performance

11.2 Monitoring for Adverse Events

At each visit, after the subject has had the opportunity to spontaneously mention any problems, the investigator should inquire about AEs by asking the standard questions shown below and report as applicable:

• "Have you had any health problems since your last study visit?"

• "Have there been any changes in the medications you take because of a new health issue or worsening of an existing health issue since your last study visit?"

In addition, changes in any protocol-specific parameters and/or questionnaires evaluated during the study are to be reviewed by the investigator. Any untoward (unfavorable and unintended) change in a protocol-specific parameter or questionnaire response that is clinically relevant, in the opinion of the investigator, is to be reported as an AE. These clinically relevant changes will be reported regardless of causality.

11.3 Procedures for Recording and Reporting

AEs are collected from the time of informed consent. Any preexisting medical conditions or signs/symptoms present in a subject prior to the start of the study (i.e., before informed consent is signed) are not considered AEs in the study and should be recorded in the Medical History section of the eCRF.

For each recorded event, the ADEs and SAEs documentation must include date of occurrence, severity, treatment (if applicable), outcome, and assessments of the seriousness and causality. In addition, the investigator must document all device deficiencies reported or observed with test and comparator products on the Device Deficiency eCRF. The site must submit all available information on ADEs, SAEs, and device deficiencies to the study sponsor as follows:

- All SAEs must be reported immediately (within 24 hours) of the investigator's or site's awareness.
- ADEs that do not meet seriousness criteria and device deficiencies must be reported within 10 calendar days of the investigator's or site's awareness.
- A printed copy of the completed *Serious Adverse Event and Adverse Device Effect* and/or *Device Deficiency* eCRF must be included with product returns.
- Additional relevant information after initial reporting must be entered into the eCRF as soon as the data become available.
- Document any changes to concomitant medications on the appropriate eCRFs.
- Document all relevant information from Discharge Summary, Autopsy Report, Certificate of Death etc., if applicable, in narrative section of the *Serious Adverse Event and Adverse Device Effect* eCRF.

Note: Should the EDC system become nonoperational, the site must complete the appropriate paper *Serious Adverse Event and Adverse Device Effect* and/or *Device Deficiency* Form. The

completed form is emailed to the study sponsor at [contact] according to the timelines outlined above; however, the reported information must be entered into the EDC system once it becomes operational.

In addition to recording all AEs into the EDC system, any AEs and device deficiencies for non-study marketed devices/products will be considered and processed as spontaneous following the postmarket vigilance procedures and should be communicated to the device's/product's manufacturer as per local requirements.

Study sponsor representatives may be contacted for any protocol related question and their contact information is provided in the Manual of Procedures that accompanies this protocol.

Further, depending upon the nature of the AE or device deficiency being reported, the study sponsor may request copies of applicable portions of the subject's medical records. The investigator must also report all AEs and device deficiencies that could have led to a SADE according to the requirements of regulatory authorities or IRB/IEC.

Intensity and Causality Assessments

Where appropriate, the investigator must assess the intensity (severity) of the AE based on medical judgment with consideration of any subjective symptom(s), as defined below:

Intensity (Severity)

Mild	An AE is mild if the subject is aware of but can easily tolerate the sign or			
	symptom.			
Moderate	An AE is moderate if the sign or symptom results in discomfort significant			
	enough to cause interference with the subject's usual activities.			
Severe	An AE is severe if the sign or symptom is incapacitating and results in the			
	subject's inability to work or engage in their usual activities.			

For every AE in the study, the investigator must assess the causality (Related or Not Related to the medical device or study procedure). An assessment of causality will also be performed by study sponsor utilizing the same definitions, as shown below:

Causality

Related An AE classified as related may be either definitely related or possibly related where a direct cause and effect relationship with the medical device or study procedure has not been demonstrated, but there is a reasonable possibility that the AE was caused by the medical device or study procedure.

Not Related An AE classified as not related may either be definitely unrelated or simply unlikely to be related (i.e., there are other more likely causes for the AE).

The study sponsor will assess the AEs and may upgrade the investigator's assessment of seriousness and/or causality. The study sponsor will notify the investigator of any AEs that is upgraded from nonserious to serious or from unrelated to related.

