9.4 Treatment masking

This study is ONLY assessor-masked for manifest refraction, VA, **manual** and contrast sensitivity. To minimize bias, Alcon personnel (including biostatistics, masked data manager, and clinical project lead) will also be masked to the IOLs that have been previously implanted in the subject, to the extent possible. All other members associated with the study (at the site and the study sponsor) are unmasked.

This level of masking will be maintained throughout the conduct of the study. Unmasking will occur only after all planned study data have been validated, and the database locked.

Masked study personnel must avoid seeking information that may compromise masking. Unmasked study personnel must not disseminate information that is potentially unmasking to any masked personnel. The masked and unmasked site personnel must coordinate all study activities as necessary to protect masking and minimize bias during the study. Any unmasking of assessor or subject must be reported to Alcon.

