10.1 Informed Consent and Screening

The investigator or delegate must explain the purpose and nature of the study, and have the subject read, sign, and date the IRB/IEC-approved informed consent document. The subject must sign the ICF BEFORE any study-specific procedures or assessments can be performed, including study-specific screening procedures. Additionally, have the individual obtaining consent from the subject and a witness, if applicable, sign and date the informed consent document.

The investigator or delegate must provide a copy of the signed document to the subject and place the original signed document in the subject's chart, or provide documentation as required by local regulations.

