10.2.2 Medical History and Concomitant Medication

Medical History and Concomitant Medications will be documented in the subject's source but will not be collected in the eCRF for this study.

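### Do the AE and SAE tables depend on how a site treats a finding first seen at the Visit 0 examinations?

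*Protocol*

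**What the plan says.** Protocol Table 3-1 schedules slit lamp, tonometry, dilated fundus, PCO, capsulotomy, IOL observations and IOL position at Visit 0 only. SAP 5.3.6 to 5.3.12 repeat that timing. Consent comes first: "The subject must sign the ICF BEFORE any study-specific procedures or assessments can be performed" (Protocol 10.1).

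Four protocol sections bear on whether a finding from those examinations is an AE:

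- 10.2.20: "Assess and record any adverse events that are observed or reported since the time of consent".
- 11.1, for six named ocular events including cystoid macular edema and retinal detachment: "the investigator must report any occurrence of the following as an SAE".
- 11.2: the standard question is "Have you had any health problems since your last study visit", and the investigator reports "Any untoward (unfavorable and unintended) change in a protocol-specific parameter or questionnaire response that is clinically relevant".
- 11.3: conditions or signs present before consent "are not considered AEs in the study and should be recorded in the Medical History section of the eCRF".

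On medical history, Protocol 10.2.2 says that it "will not be collected in the eCRF for this study", and footnote c of the schedules in both documents says source only.

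SAP 5.3.2 tabulates AEs, ADEs and SAEs by IOL group and states no onset cut-off. SAP 5.3 restricts the subject listings to AEs occurring after consent, as does Protocol 12.6.1.2. On masking, apart from the refraction, VA and contrast-sensitivity assessors (one further item is blacked out) and certain sponsor personnel, "All other members associated with the study (at the site and the study sponsor) are unmasked" (Protocol 9.4).

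**The concern.** A sign first seen at Visit 0 is observed after consent but will usually have begun before it. If 10.2.20 turns on the date of observation and 11.3 on the date of onset, the same finding is counted at one site and not at another. The sharpest case is cystoid macular edema found at the Visit 0 fundus examination. It looks like an SAE under 11.1, with 24-hour reporting, yet is not an AE under 11.3 if judged to pre-date consent. Section 11.2 offers little help, because Visit 0 has no previous study visit and no scheduled earlier value from which to measure a change. The place 11.3 assigns to pre-existing findings is also one that 10.2.2 says is not collected.

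The planned AE and SAE percentages by lens would be at stake. SAP 1.1.4 uses them to assess one lens against the other in a nonrandomized study. Because the person who classifies a finding may know the lens, the handling could in principle differ between arms.

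**Working it through.** The documents state no AE rate or count, so there is no figure to reproduce. The check is a reading of the text followed by a bound on the effect.

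**Reading the sections together**

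1. Section 11.3 is the only place that addresses pre-consent conditions. It excludes signs present before consent, not every sign first seen at Visit 0.
2. Section 10.2.20 concerns adverse events, a term that 11.3 limits. Its second paragraph starts collection at the signing of consent, as 11.3 does.
3. The Glossary defines an SAE as a kind of adverse event. The 11.1 list can therefore be read as fixing the seriousness of something that is already an AE.
4. SAP 5.3.2 says AEs are collected at Visits 0 and 1. That is compatible with onset after consent, and the SAP need not repeat the protocol's definition. The SAP 5.3 listings already carry the onset condition.
5. Table 3-1 puts consent and the examinations at the same visit, Study Day 0. Under the onset rule the examinations would contribute almost no AEs, and the tables would describe new events over the planned 1 to 14 days to Visit 1. As a share of time since the second implant, that is 1/180 = 0.6% to 14/90 = 15.6%.
6. Section 11.3 also asks for concomitant medication changes on eCRFs, although 10.2.2 keeps those in source as well. Two mismatches of the same kind in one section suggest standard text that was not adapted to this study. That is an inference.

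**Size, if sites nevertheless differed**

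Inputs: about 105 enrolled per arm and 210 in all (Protocol 12.8). The safety set is every enrolled, bilaterally implanted subject (Protocol 12.2), so screen failures stay in. The share *q* of subjects with a disputed finding is an assumption.

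- Step per subject: 1/105 = 0.95 percentage points.
- Expected disputed subjects per arm, 105 × *q*: 0.5 at *q* = 0.5%, 1.1 at 1%, 3.2 at 3%.
- Chance of at least one in 210, 1 − (1 − *q*)^210: 65.1%, 87.9% and 99.8%.
- Spurious difference between arms, taking the same *q* in both: *q* × (s_T − s_C), where s_T and s_C are the shares of test and comparator subjects handled under the broader reading. If s_T = s_C, it is 0. It reaches *q* (0.5 to 3 points) only if s_T = 1 and s_C = 0.

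The chance of at least one disputed subject says the tables might differ somewhere. It does not measure importance. On the last line, Protocol 8 recommends, without requiring, that each site aim for equal numbers of both lenses. A habit that belongs to a site would then tend to affect both arms alike.

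**The case for a change.** The strongest case is that neither document states this precedence. Section 11.1 introduces its list as additional to AEs that meet the definitions, which can be read as reaching beyond them, and it sets no onset limit. Subjects found to have such an event may fail screening, but they stay in the safety set. The SAP 5.3.6 to 5.3.12 tables carry neither seriousness nor causality, so they do not replace the AE, ADE and SAE tables. Stating a rule, splitting the tables by onset and having a masked reviewer check Visit 0 findings against AE records would need no new visit or examination.

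Part of this stands. A listed event judged to pre-date consent could be handled in two ways, which also bears on the 24-hour SAE report. Sections 10.2.2 and 11.3 do disagree on where medical history is kept.

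The rest is weaker. Protocol 10.3 lets slit lamp, tonometry and fundus examinations be repeated at unscheduled visits, and medical history is reviewed in source, so an investigator may have something against which to date a finding. No passage suggests that staff classify by lens.

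The remedy also gains little. Under 11.3, a table of pre-consent findings would be empty, because such findings are not AEs and would not be entered as AEs. The masked check would need an extra reviewer and onset information that is held only in source.

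**Conclusion.** No change to the plan follows. The AE tables are sound under the onset rule in 11.3, and the other sections can be read consistently with it. An analyst who applies one AE definition to both the SAP 5.3.2 tables and the SAP 5.3 listings fills the gap in the obvious way. The Visit 0 findings are still reported by IOL group or lens model. Protocol 12.6.1.1 and SAP 5.2 plan no safety hypothesis test, and the protocol's safety objective is only to describe AE rates.

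What remains is clerical: where medical history is held (10.2.2 against 11.3), and the silence of 11.1 on the onset exclusion. These passages should agree, and a clarification to sites would be enough.

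The size is 0.95 points per disputed subject in an arm. The 0.5 to 3 point difference between arms is a ceiling under assumed prevalences and wholly opposite handling, and nothing in the documents supports that pattern. The conclusion rests on 11.3 governing what counts as an AE. The Manual of Procedures and the AE form were not available and may already settle how sites handle such findings.

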11.4 Return product analysis

Study sponsor representatives and their contact information are provided in the MOP that accompanies this protocol.

Should a product need to be returned, include the Complaint # which will be provided by study sponsor after the case is entered in the study sponsor's Global Product Complaint Management System (GPCMS).

Return any recoverable Alcon Product associated with a product related AE (ADE, SADE) or device deficiency to the sponsor. Procedures vary by country, so investigators must contact their assigned monitor for detailed guidance. Follow biohazard regulations if the product has touched the eye (i.e., place the product in a biohazard labeled bag). Include the SAE/ADE or device deficiency electronic case report form (eCRF) in the return package. Maintain a copy of shipment tracking information and all documents submitted with the product.

11.5 Unmasking of the Study Treatment

This study is assessor-masked for manifest refraction, VA, **manual** and contrast sensitivity. To minimize bias, Alcon personnel (including biostatistics, masked data manager, and clinical project lead) will also be masked to the IOLs that have been previously implanted in the subject, to the extent possible. All other members associated with the study (at the site and the study sponsor) are unmasked.

This level of masking will be maintained throughout the conduct of the study. Unmasking will occur only after all planned study data have been validated, and the database locked.

11.6 Follow-Up of Subjects with Adverse Events

The investigator is responsible for adequate and safe medical care of subjects during the study and for ensuring that appropriate medical care and relevant follow-up procedures are maintained after the study.

The investigator should provide the study sponsor with any new safety information (which includes new AEs and changes to previously reported AEs) that may affect the safety evaluation of the device. For AEs that are unresolved/ ongoing at time of subject exit from study, any additional information received at follow-up should be documented in the eCRFs up to study completion (i.e., database lock).

All complaints received after study completion will be considered and processed as spontaneous (following the postmarket vigilance procedures) and should be communicated to the medical device's manufacturer as per local requirements.

The investigator should also report complaints on non-Alcon products directly to the manufacturer as per the manufacturer's instructions or local regulatory requirements.

Pregnancy in the Clinical Study: Pregnancy is not reportable as an AE; however, complications may be reportable and will be decided on a case-by-case basis.

